## 2.1 Study Rationale

A first study, VYF01, aiming to assess the safety, viremia and immune responses of 3 dosages of vYF, compared to YF-VAX, as a control vaccine, is ongoing in the USA. A second planned study, VYF02, aims to assess the non-inferiority of the immune response of the investigational vaccine candidate vYF to the licensed YF-VAX vaccine in adults in the USA.

The proposed third study, VYF03, is a Phase II, randomized, observer-blind, active-controlled (Stamaril) study to assess the non-inferiority of the immune response, in terms of seroconversion rates, of the investigational vaccine candidate vYF to the licensed Stamaril, in adults aged 18 years up to 60 years in EU. The safety and immunogenicity profile of vYF in a cohort of participants of Chinese origin living in Asia will also be presented. The study will also assess the immunogenicity profiles (seroprotection, GMT and GMTR) and the safety profiles of vYF and Stamaril.

In EU, it is planned to enroll 570 participants into 2 groups in a 2:1 ratio: 380 participants will be administered vYF and 190 participants will be administered Stamaril on D01. In Asia, it is planned to enroll 120 participants also distributed into 2 groups in a 2:1 ratio: 80 participants will be administered vYF and 40 participants will be administered Stamaril on D01.

The persistence of the immune response over time, up to 5 years post-vaccination, will be assessed yearly.

VYF03 assessment will be based on immunogenicity and safety profiles of the vYF vaccine in comparison to Stamaril, which is the current YF vaccine licensed in more than 100 countries (except USA, Canada, and Japan).

The YF neutralizing antibody titers will be determined in a microneutralization (MN) assay that was developed by Sanofi Pasteur and currently in use in VYF01. An interim analysis on the first 37 randomized participants (36 of them vaccinated with either vYF 4 Log CCID50/dose, 5 Log CCID50/dose, 6 Log CCID50/dose, or YF-VAX) shows that GMTs well above the threshold of protection (10, 1/dil) were observed in all vaccine groups on D28 post vaccine administration (Per-Protocol analysis in YF-naïve populationa) and that 100% of YF-naïve participants seroconvertedb and were seroprotected on D28. The satisfactory safety profile of all vYF dosage groups and the measurement of quantified viremia over time from D01 to D15 completed the interim analysis. Therefore, the dosage of 5 Log CCID50/dose is deemed appropriate for the next phases of the clinical development of vYF, starting with VYF02, which is the first non-inferiority study in adults.

VYF03 is designed to assess the immune response and the maintenance of the antibody titers over time, up to 5-years post vaccine administration as the existing YF vaccines are well known for inducing a long-lasting immunity. In addition, a subset of participants will be assessed on D11 to describe the early immune response induced in the 2 vaccine groups.

a YF-naïve population, or YF negative population, corresponds to participants with no pre-existing (ie, no detectable as below LLOQ equal to 10 (1/dil) which also defines the threshold for protection) Ab titers. Those participants are given a value equal to half LLOQ, ie, 5 (1/dil).

\_

<sup>b In VYF01, seroconversion is achieved for a 4-fold increase as compared to pre-vaccination value; and in YF-naïve participants seroconversion is achieved for a value equal or greater than 40 (1/dil).

The AESIs that are considered for the development of vYF were defined based on the knowledge of those associated to existing YF vaccines licensed by Sanofi Pasteur (YF-VAX and Stamaril):

- Serious hypersensitivity/allergic reactions
- Organ failure/serious viscerotropic events
- Serious neurologic events

## 2.2 Background

As with the existing licensed YF vaccines, the new vYF vaccine is a live-attenuated vaccine derived from the wild-type Asibi strain. It is being developed as an alternative to the egg-based vaccines, as it is manufactured in extensively characterized Vero cells, in the absence of animal serum, hence potentially also increasing vaccine safety.

Therefore, it should facilitate the management of YF vaccine outbreaks and epidemics which is challenging due to limited amounts of YF vaccine stock. The development of a new attenuated live vYF vaccine, manufactured in extensively characterized Vero cells represents major progress. The safety, immunogenicity and clinical efficacy of this new vaccine is planned to be compared to the Sanofi Pasteur licensed Stamaril YF vaccine, and VYF03 is the first non-inferiority study in adult populations in EU.

### 2.3 Benefit/Risk Assessment

More detailed information about the known and expected benefits and risks, reasonably expected adverse events (AEs), the potential risks, and uncertainties of vYF vaccine candidate vaccine may be found in the Investigator's Brochure (IB).

## 2.3.1 Risks from Study Participation

The potential risks of clinical significance and risk management are summarized in Table 2.1.

Table 2.1: Potential risks of clinical significance and risk management

Potential Risk of Clinical Significance	Summary of Data/Rationale for Risk	Risk Management			
Investigated Vaccine: vYF					
The following AESIs have been defined for this clinical development program based upon the prior experience with YF vaccines:					
Serious hypersensitivity/allergic reactions (eg anaphylaxis)	All vaccines have the potential to cause allergic reactions or anaphylaxis in individuals who may be sensitized to components of the vaccine.	Exclusion criteria E07 (Known systemic hypersensitivity to any of the vaccine components, or history of a life-threatening reaction to the vaccines used in the study or to a vaccine containing any of the same substances)  30-minute observation period after vaccination for early detection and treatment			
Organ failure/serious viscerotropic events (YF vaccine-associated viscerotropic disease  YEL-AVD]) Serious neurologic events (YF vaccine-associated neurotropic disease  YEL-AND]) YEL-AVD and YEL-AND are theoretical risks for the studied vaccine, according to preclinical tests.	Serious AE related to YF vaccines are YEL-AVD and YEL-AND. They are very rare and thus unlikely to be seen in the setting of a clinical trial.	Exclusion criteria E10 (personal or family history of thymic pathology [thymoma, thymectomy, or myasthenia]) for those at increased risk.  Observation period of 28 days after vaccination for early detection and treatment.  Addressed in the "Operating Guidelines for Assessing Viscerotropic and Neurotropic AEs" in studies using YF vaccines (standalone guidance provided to the Investigational sites before the start of the study).			

Potential Risk of Clinical Significance	Summary of Data/Rationale for Risk	Risk Management			
Comparator: Stamaril					
Severe allergic reactions (eg, anaphylaxis) may occur following the use of Stamaril, even in individuals with no prior history of hypersensitivity to the vaccine components.	Identified and potential risks observed in post-marketing surveillance.	Exclusion criteria E07 (Known systemic hypersensitivity to any of the vaccine components, or history of a life-threatening reaction to the vaccines used in the study or to a vaccine containing any of the same substances)  Stamaril is contraindicated in anyone with a history of acute hypersensitivity reaction to any component of the vaccine, in infants less than 9 months of age due to an increased risk of encephalitis, in individuals with severe immunosuppression  Exclusion/inclusion criteria take in account contraindications, warnings and precautions as defined in product label. See  Section 5 of this document.  30-minute observation period after vaccination for early detection and treatment.			
Organ failure/serious viscerotropic events (YEL- AVD) Serious neurologic events (YEL- AND) There is an increased risk of severe systemic adverse reactions to Stamaril in individuals 60 years of age and older and in immunocompromised individuals.	Serious AE related to YF vaccines are YEL-AVD and YEL-AND. They are very rare and thus unlikely to be seen in the setting of a clinical trial. Refer to the IB Section 6 for more information regarding the data from previous experience	Exclusion criterion E10 (Personal or family history of thymic pathology (thymoma, thymectomy, or myasthenia]) for those at increased risk.  Observation period within 28 days after vaccination for early detection and treatment.  Inclusion criteria I01 state the upper limit of age up 60 years on the day of inclusion a Exclusion criterion E05 (Known or suspected congenital or acquired immunodeficiency; or receipt of immunosuppressive therapy)  Addressed in:			

a "18 to 60 years" means from the day of the 18th birthday up to the day before the 60th birthday

Potential Risk of Clinical Significance	Summary of Data/Rationale for Risk	Risk Management
		-IB (administration precautions, potential adverse events), defined AESI in the trial.  "Operating Guidelines for Assessing Viscerotropic and Neurotropic Adverse Events in studies using YF vaccines" (standalone guidance provided to the Investigational sites before the start of the study)
	Study Procedures	•
Vasovagal reactions (syncope), or psychogenic reactions to needle (vaccine injection or blood sampling)	Anxiety-related reactions can occur following, or even before, any vaccination as a psychogenic response to the needle injection or blood draw, and may be accompanied by several neurological signs such as transient visual disturbance, paresthesia or seizure-like activity	30-minute observation period after vaccination for early detection and treatment

# 2.3.2 Benefits from Study Participation

This study is experimental research and there is no guarantee that participants enrolled in VYF03 will get any benefit.

vYF is a next-generation live-attenuated YF vaccine produced on serum-free Vero cells without any component of animal origin. vYF has been developed to induce a life-long immunity against YF and to be at least as immunogenic as other licensed YF-17D vaccines and well-tolerated.

Participants enrolled in VYF03 will be followed up yearly up to 5 years post vaccine administration to assess the maintenance over time of the immune response.

It is expected that participants enrolled in VYF03 will be protected against YF, which means that both the new investigational vaccine as well as the current licensed Stamaril vaccine, elicit a safe, protecting, and long-lasting immune response.

### International Certificate of Vaccination or Prophylaxis for YF Vaccination

At the end of the first interim analysis and at the end of the study, the Investigators will be provided with individual listings detailing for each participant the vaccine group assignment and the neutralizing antibody titers at the successive time points. Participants are responsible for

contacting the study site to obtain this information about which study group they were assigned to and which vaccine they received.

VYF03

Those participants enrolled in the Stamaril group can be provided by the investigational site with the ICVP for YF vaccination; and those participants enrolled in a vYF group would be informed that they need to obtain a licensed YF vaccine prior to travel to endemic areas.

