## **6.3.2** Blinding and Code-breaking Procedures

The VYF03 study is a Phase II, randomized, observer-blind, active-controlled, non-inferiority study to the Stamaril control vaccine.

The study will be performed in a modified double-blind fashion: Sponsor, Investigators and Study staff who conduct the safety assessments, and the participant will not know which vaccine is administered.

Only the study staff who prepare and/or administer the vaccine and who are not involved in safety evaluations ("vaccinator") will know which vaccine is administered. The "vaccinator" or authorized designee will have to ensure that the documents on randomization are stored in a secure place where only he/she has access.

The code may be broken in the event of an AE only when the identification of the vaccine received could influence the treatment of the participant. Code-breaking should be limited to the participant(s) experiencing the AE.

The blind can be broken by the Investigator or a delegate through the IRT system, as explained in the code-breaking procedures described in the Operating Guidelines. Once the emergency has been addressed by the site, the Investigator or a delegate must notify the Sanofi Pasteur Responsible Medical Officer (RMO) if a participant's code was broken. All contact attempts with the Sponsor prior to unblinding are to be documented in the source documents, and the codebreaking case report form (CRF) is to be completed.

The Institutional Review Boards (IRB)/Independent Ethics Committees (IEC) must be notified of the code-breaking, in accordance with local regulations. All documentation pertaining to the event must be retained in the site's study records, and in the Sanofi Pasteur files. Any intentional or unintentional code-breaking must be reported, documented, and explained, and the name of the person who requested it must be provided to the Sponsor.

A request for the code to be broken may also be made:

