#### SAEs

Information on SAEs will be collected and assessed throughout the study, from inclusion at D01 until 6 months after vaccination, and related SAEs and fatal SAEs throughout the study, up to 5 years after vaccination. However, before the study intervention administration, only SAEs related to study procedures are to be collected.

Medical occurrences that begin before the start of study intervention but after obtaining informed consent will not be recorded on the AE section of the case report book (CRF).

All SAEs will be recorded and reported to the Sponsor or designee immediately and under no circumstance should this exceed 24 hours, as indicated in Appendix 10.3. The Investigator will submit any updated SAE data to the Sponsor within 24 hours of it being available.

Investigators are not obligated to actively seek AE or SAE after conclusion of the study participation. However, if the Investigator learns of any SAE, including a death, at any time after a participant has been discharged from the study, and he/she considers the event to be reasonably related to the study intervention or study participation, the Investigator must promptly notify the Sponsor.

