# 9.5 Interim Analyses

#### Interim Analyses

Six statistical analyses will be performed on data obtained from all participants.

The first interim analysis will be performed on the immunogenicity results obtained up to the D29 visit and safety data obtained up to the 6-month follow-up visit, then the successive interim analyses will be performed on data connected up to Y1 visit and not yet analyzed, then every year on the data gathered at each yearly visit up to 4 years after YF vaccine administration; these results will be presented in an interim clinical study report (CSR) (immunogenicity data up to D29 and safety data up to M6) or CSR addendum (up to Y4). In addition, the first interim analysis will be performed on immunogenicity and safety data gathered on all EU participants enrolled and followed up, even in case the submission/approval in Asian countries and/or the recruitment of participants of Chinese origin is delayed as compared to that in EU. As a consequence, an interim CSR might be produced to present the analysis on participants enrolled in EU only.

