#### 10.2 Appendix: Clinical Laboratory Tests

A urine human chorionic gonadotropin (hCG) pregnancy test (as needed for women of childbearing potential) will be performed before vaccination at D01 (Visit 1) and at D29 (Visit 4). Pregnancy Testing is compulsory at V01 since pregnant women cannot be included in this study.

Additional tests may be performed at any time during the study as determined necessary by the Investigator or required by local regulations.

Investigators must document their review of each laboratory safety report.

Laboratory results that could unblind the study will not be reported to Investigational sites until the study has been unblinded for the first interim analysis, in order to allow the Investigators to provide the ICVP for YF vaccination to the participants randomized in the Stamaril group.

Laboratory results that could unblind the study will not be reported to investigative sites or other blinded personnel until the study has been unblinded.

VYF03

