#### **Assessment of Causal Relationship**

By convention, all AEs reported at the injection site (either solicited or unsolicited) and all solicited systemic AEs are considered to be related to the IMP (see definition in Section 6) and therefore are referred to as reactions and do not require the Investigator's opinion on relatedness.

• Causal relationship of unsolicited systemic AEs and SAEs will be recorded as follows:

- For non-serious unsolicited systemic AEs (except for non-serious AESIs), relationship to study intervention will usually be assessed by the Investigator only.
- For SAEs and non-serious AESIs, relationship to study intervention will be assessed by both the Investigator and the Sponsor (except for injection site reactions which will be related by default). Sponsor assessment is entered in the GPV database only.
- For SAEs only, the causal relationship to study procedures (related/not related to study procedures) will be assessed by both the Investigator and the Sponsor. Sponsor assessment is entered in the GPV database only.
- The Investigator will assess the causal relationship between each unsolicited systemic AE and the study intervention administered as either not related or related, based on the following definitions:
  - Not related The AE is clearly / most probably caused by other etiologies such as participant's underlying condition, therapeutic intervention, or concomitant therapy; or the delay between vaccination and the onset of the AE is incompatible with a causal relationship; or the AE started before vaccination (screening phase, if applicable)
  - Related There is a "reasonable possibility" that the AE was caused by the study intervention administered, meaning that there are facts (evidence) or arguments to suggest a causal relationship
- The Investigator will use clinical judgment to determine the relationship.
- Alternative causes, such as underlying disease(s), concomitant therapy, and other risk factors, as well as the temporal relationship of the event to study intervention administration will be considered and investigated.
- The Investigator will also consult the IB and/or Product Information, for marketed products, in his/her assessment.
- For each AE/SAE, the Investigator must document in the medical notes that he/she has reviewed the AE/SAE and has provided an assessment of causal relationship.

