## 5.4 Interim / Preliminary Analysis

Six statistical analyses will be performed on data obtained from all participants.

The first interim analysis will be performed on immunogenicity results and safety data obtained up to the 6-month follow-up visit with all available data collected, cleaned and locked. However, for regulatory purposes, it might be decided to analyze separately the D01-D29 and M6 follow-up periods. This planned analysis will require the unblinding of data. Once the interim database lock has been conducted, the trial statistician will break the blind and will conduct the statistical analysis.

Then the successive interim analyses will be performed on data collected up to Y1 visit and not yet analyzed, then every year on the data gathered at each yearly visit up to 4 years after YF vaccine administration; these results will be presented in an interim clinical study report (CSR) (immunogenicity data up to D29 and safety data up to M6) or CSR addendum (up to Y4).

In addition, the first interim analysis will be performed on immunogenicity and safety data gathered on all EU participants enrolled and followed up, even in case the submission/approval in Asian countries and/or the recruitment of participants of Chinese origin is delayed as compared to that in EU. As a consequence, an interim CSR might be produced to present the analysis on participants enrolled in EU only.

The final analysis will be performed at the end of the follow-up (5 years after YF vaccine injection).

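### After the first interim analysis, Investigators who hold the vaccine assignments decide whether a late non-fatal SAE is collected at all, while Protocol 6.3.2 still describes them as blinded

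*Protocol*

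**What the plan says.** **Blinding.** Protocol 6.3.2 says: "Sponsor, Investigators and Study staff who conduct the safety assessments, and the participant will not know which vaccine is administered". Only staff who prepare or give the vaccine, and who take no part in safety evaluation, know the assignment. That section does not say when the blind ends.

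**Disclosure.** Protocol 2.3.2, under the vaccination-certificate heading, says that at the end of the first interim analysis and again at the end of the study "the Investigators will be provided with individual listings detailing for each participant the vaccine group assignment", with titers at each time point. Protocol 10.2 agrees: laboratory results that could unblind "will not be reported to Investigational sites until the study has been unblinded for the first interim analysis", so that certificates can be issued to Stamaril recipients.

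**Timing.** Protocol 9.5 bases the first interim on D29 immunogenicity and "safety data obtained up to the 6-month follow-up visit". SAP 5.4 adds: "Once the interim database lock has been conducted, the trial statistician will break the blind".

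**Collection.** Protocol 8.3.1 collects SAEs "from inclusion at D01 until 6 months after vaccination, and related SAEs and fatal SAEs throughout the study, up to 5 years after vaccination". AESI collection stops at month 6.

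**Causality.** Protocol 10.3.3 says: "The Investigator will assess the causal relationship between each unsolicited systemic AE and the study intervention administered as either not related or related". This must be done before an SAE is first sent to the Sponsor. The Sponsor also assesses SAEs, but its view is held only in the pharmacovigilance database.

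**Analysis.** Related SAEs and deaths to 5 years form a secondary safety endpoint (Protocol Table 3.1). SAP 4.2.2.4 takes related SAEs over the whole study as one period. SAP 4.2.2.11 uses the relationship field as collected.

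**The concern.** Each provision is ordinary when read alone. Together they mean that, once the listings have been issued, knowledge of the vaccine can affect whether a non-fatal SAE enters the database, not only how it is labelled. An Investigator might attribute a late event more readily to an investigational vaccine, or less readily to a long-licensed one. The documents give no way to tell which tendency would prevail.

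The safety objective is a description of vYF in comparison with Stamaril. Related SAEs are rare, so a few attribution decisions can produce or remove an apparent difference between arms. The usual safeguard is blinded re-adjudication of all SAEs. It is weakened here because events judged unrelated after month 6 fall outside the collection rule.

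**Working it through.** The plan gives no figure to reproduce. The check has three parts.

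**1. Who decides what, and in which period (first interim run as planned)**

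| Period | Non-fatal SAEs collected | Does the Investigator hold the listings? |
|---|---|---|
| D01 to M6 | All, related or not | No |
| M6 until the listings are issued | Only if judged related | No |
| Listings issued, to Y5 | Only if judged related | Yes |

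Only the third row combines the relatedness condition with an unblinded assessor. Three provisions might have offset it, and none does:
- The Sponsor's second causality assessment covers only events already sent to it.
- AESIs count whether related or not (Protocol 8.3.6), but their collection has ended by then.
- Neither the Protocol nor the SAP provides a blinded causality assessor, or a split of related SAEs at unblinding.

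**2. Share of follow-up in the third row**

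The documents give neither the enrolment length E nor the lag L from the last month-6 visit to the listings. Assumed ranges: E = 0 to 18 months, L = 1 to 6 months. Follow-up is 60 months, and M6 to Y5 is 54 months.

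Month of unblinding after a participant's own D01:
- first enrolled: t = 6 + E + L
- last enrolled: t = 6 + L

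Share of the 5 years = (60 − t)/60. Share of M6 to Y5 = (60 − t)/54.

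| Participant | E, L | t | Share of 5 years | Share of M6 to Y5 |
|---|---|---|---|---|
| First or last enrolled | 0, 1 | 7 | 53/60 = 88% | 53/54 = 98% |
| First enrolled | 18, 6 | 30 | 30/60 = 50% | 30/54 = 56% |
| Last enrolled | any E, L = 6 | 12 | 48/60 = 80% | 48/54 = 89% |

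The range is 50% to 88% of the 5 years for the first enrolled and 80% to 88% for the last enrolled. A figure of 54/60 = 90% would need the listings to be issued on the day of the participant's month-6 visit.

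**3. How sensitive the endpoint is to one decision**

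Inputs: planned groups of 460 (vYF) and 230 (Stamaril) from Protocol 9.2, and the Clopper-Pearson 95% interval from Protocol 9.4.2. With no events the upper limit is 1 − 0.025^(1/n).

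| Related SAEs | Rate | 95% CI |
|---|---|---|
| 0/460 | 0.00% | 0.00 to 0.80 |
| 1/460 | 0.22% | 0.01 to 1.21 |
| 0/230 | 0.00% | 0.00 to 1.59 |
| 1/230 | 0.43% | 0.01 to 2.40 |

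One event kept or dropped moves an arm between no related SAEs and a non-zero rate. The intervals are wide and overlap, so this shows sensitivity of the description and is not an estimate of bias.

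**The case against.** The strongest reply is that the unblinding is deliberate. Protocol 10.2 states its purpose, and Protocol 2.3.2 explains why each group needs the information: Stamaril recipients can receive a certificate, and vYF recipients learn that they need a licensed vaccine before travel to endemic areas. The endpoint is secondary and descriptive, no safety hypothesis is tested, and deaths are collected regardless of cause.

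Most of this stands, and it limits the weight of the point. It does not justify a general release to the people who judge causality. Protocol 2.3.2 already makes participants responsible for contacting the site, so release on request keeps that route open.

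Four stronger readings are tempting, but the documents do not support them:
- **That the whole 5-year endpoint is unblinded.** As planned, D01 to M6 is blinded with every SAE collected, and early enrollees stay blinded beyond M6 until the listings are issued.
- **That every Investigator sees every participant in the trial.** Protocol 2.3.2 does not say whether listings cross sites. The problem is the same for an Investigator's own participants.
- **That lost events can never be recovered.** Investigators ask about other AEs at each visit (Protocol 8.2), must document causality in the medical notes (10.3.3), and keep records for 25 years (10.1.7). Source review might recover some.
- **That a particular bias ratio follows.** Any such ratio only returns the relatedness rates assumed for each arm.

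It can also be objected that a before/after-disclosure table conditions on a self-selected event after randomization and will hold few cases. That is correct, and the table can only be a descriptive aid.

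**Conclusion.** The point holds in limited form. After the first interim, collection of non-fatal SAEs depends on a causality judgement by Investigators who have been given the assignments, and Protocol 6.3.2 does not say so. About 50% to 88% of each participant's 5 years is affected under the assumed enrolment and lag ranges. The true share is not derivable from the documents, and neither is the size or direction of any bias.

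The primary D29 analysis and all-cause deaths are untouched. SAEs to month 6 are untouched provided that the listings follow the month-6 interim. SAP 5.4 allows D01 to D29 to be analyzed separately. If the listings followed that earlier analysis, unblinding would come sooner.

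The change should be made because it is cheap and most of the exposure is avoidable. It is not a threat to the trial's main conclusion.

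**What to change.** 1. **Protocol 2.3.2 and 10.2:** send the listings and unblinding laboratory results to the unblinded site role already defined in 6.3.2. Release an assignment only when that participant asks, so that the Investigator judging SAE causality otherwise stays blinded.
2. **CRF:** record the date of each disclosure.
3. **Protocol 6.3.2:** state when, and for whom, the blind ends.
4. **SAP 4.2.2.4:** report related SAEs separately before and after disclosure (or before and after first-interim unblinding, if the general release is kept). Label the table descriptive and the later part open-label, and show all-cause deaths alongside.

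The cost is wording in the Protocol and Operating Guidelines, one CRF date and one table split. The unblinded site role must stay open during follow-up, participants who ask may still unblind their Investigator, and the split table will hold few events.

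This leaves the relatedness condition in place and blinds most of the judgements that operate it. Removing the condition would mean collecting all SAEs to year 5, which is a larger burden on sites.
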